Reference Therapy, Dosage, and Mode of Administration	Cognitive Behavior Therapy for Insomnia (CBT-I) Focus of Attention (FOA) Combined CBT-I and FOA Sleep Hygiene Six sessions, one hour each, in person.
Criteria for Evaluation	
Primary Endpoint	The primary end point is completion of 6 treatment sessions and completion of the 3 month, 6 month and 12 month follow-up assessment. Improvement of insomnia outcome is measured by Self Report Sleep Measures (SRSM).
Key Secondary Endpoint	The Secondary end point is improvement outcomes.
Additional Endpoints	Safety Population: will include all randomized subjects who meet eligibility criteria and meet with their treatment provider for session 1. Intent-to-Treat Population: will include all subjects who meet with their treatment provider for session 1 and for whom the treatment provider determines the subject meets diagnostic criteria for 780.52 Insomnia Disorder. Pre-Protocol (PP) Population: will include all subjects who complete the 6 sessions of treatment as well as the 3 month, 6 month and 12 month follow up assessment. It is estimated that 80% of those who complete session 1 will complete session 6. It is estimated that 80% of those who complete session 6 will complete the 3 month, 6 month and 12 month follow up assessments. This will result in 25 participants who will have completed the entire study

Pharmacogenetics Sampling	There are no pharmacogenetics samplings.
Health Outcomes	

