	restriction will be offered. The participant will also have the option of discontinuing the treatment if they prefer this to proceeding with the alternative treatment which does not involve sleep restriction.
Pharmacokinetic Sampling	There are no pharmacokinetic samplings.
Statistical Analysis	Repeated measures analysis of variance (ANOVA) will be used to test Hypotheses 1, 2 and 3. Chi square will be used to test Hypothesis 4.

SCHEDULE OF EVALUATIONS: Study PSPC-17-01

	Screening	Randomized, Open label, sleep Hygiene Controlled 6 Week study							EOT/ ET (1 week F/U)	Safety Follow up Period		
		1	(BV)/ 2	3	4	5	6	7		8	9	10
Visit #	1	up to 14 days	(BV)/ 2	3	4	5	6	7	8	9	10	11
Study Day Weeks/Months		1W	2W	3W	4W	5W	6W	7W	7W	3M	6M	12M
Informed consent	x											
Review of Histories	x											
Medication History +Concomitant Medications	x											
Inclusion/ Exclusion	x	x	x	x	x	x	x	x	x	x	x	x
Randomization												
Assessment		x										
Questionnaire & Inventories GMS/GMS-I												
ISI	x							x	x	x		x
BDI	x							x	x	x	x	x
BAI	x							x	x	x	x	x
SRSM	x	x	x	x	x	x	x	x	x	x	x	x
WSL								x	x	x	x	x
CGI-I	x	x	x	x	x	x	x	x	x	x	x	x
CGI-S	x	x	x	x	x	x	x	x	x	x	x	x
Q-LES	x							x				
DSM-5 diagnostic Interview	x											
C-SSRS	x	x	x	x	x	x	x	x	x	x	x	x

(GMS) Goal Motivation Scale; (GMS-I) Goal Motivation Scale-Insomnia, Beck Depression Inventory (BDI); Beck Anxiety Inventory (BAI); Insomnia Severity Index (ISI); Self Report Sleep Measures (SRSM); Weekly Sleep Log (WSL);

Clinical Global Impression - Improvement (CGI-I), Clinical Global Impression – Severity scale (CGI-S)

Quality of Life Enjoyment and Satisfaction (Q-LES), End of Treatment (EOT)/Early Termination (One week F/U): (ET)

Columbia suicide severity rating scale (C-SSRS); Baseline Visit (BV)

3.0

TABLE OF CONTENTS

1.0 TITLE PAGE -----	1
2.0 SYNOPSIS AND SCHEDULE OF EVALUATIONS-----	2
3.0 TABLE OF CONTENTS-----	8
4.0 LIST OF ABBREVIATIONS-----	12
5.0 ETHICAL CONSIDERATIONS-----	13
5.1 INSTITUTIONAL REVIEW BOARD AND INDEPENDENT ETHICS-----	13
5.2 COMMITTEE ETHICAL CONDUCT OF THE STUDY -----	13
5.3 PATIENT INFORMATION AND INFORMED CONSENT -----	13
6 INVESTIGATORS AND STUDY ADMINISTRATIVE STRUCTURE-----	14
7 INTRODUCTION-----	15
8 STUDY OBJECTIVES-----	22
9 INVESTIGATIONAL PLAN-----	28
9.1 OVERALL STUDY DESIGN AND PLAN: DESCRIPTION-----	28
9.1.1 IN PERSON SCREENING AND DATA GATHERING-----	28
9.1.2 DSM-5 DIAGNOSTIC SCREENING INTERVIEW-----	28
9.1.3 SAFETY FOLLOW UP PERIOD-----	31

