complete 12 month follow-up. These subjects will then be eliminated as relates to analyses involving 12 month follow-up data. Statistical analyses will be conducted to determine whether those with missing data differ significantly from those without missing data using t test comparing the two groups on total scores on Insomnia Severity Index at pre-treatment as well as post-treatment.

STATISTICS

Repeated measures analysis of variance (2 X 4 ANOVA) will be used to test the Hypotheses 1-3, 5-10 and 11-16. Any statistically significant ANOVAs will be followed by pairwise t-test comparisons to identify between group differences. Chi square will be used to test Hypotheses 4 and 11.

SAFETY ANALYSIS

In general the potential risks for participants are minimal. The treatment approaches involved in related studies have been shown to be a safe procedure and in most of the published studies people who underwent these procedures did not report any harmful effects.

Prospective participants will be informed that it is nonetheless possible you may experience some discomforts during the treatment. These may include temporary decrease in time asleep and accompanying daytime drowsiness. Some people may become anxious while initially following the treatment procedures, with increased worry about their sleep difficulty. Anxiety and worry about sleep difficulty are in fact common among persons with insomnia. Therefore identifying and addressing these possibilities will be directly addressed during the treatment, and participants will be given guidance about what to expect and how to manage should these discomforts occur. Prospective participants will also be informed that persons with certain medical illnesses, certain psychiatric illnesses or other sleep disorders may be at increased potential risk of exacerbation of that illness. This is a possibility for participants with epilepsy, bipolar depression, parasomnia, obstructive sleep apnea or other illnesses which have excessive daytime sleepiness as a feature of the parent disorder. The participant may (or may not) be assigned to a treatment which involves sleep restriction. Sleep loss through sleep restriction may

- 1) Lower the threshold for seizures in persons with epilepsy;
- 2) Precipitate mania in bipolar participants;
- 3) Exacerbate parasomnias;
- 4) Prevent adequate ventilation in patients with obstructive sleep apnea; and/or

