9.5.1.2 EFFICACY ASSESSMENTS

The efficacy assessments (CGI -S) will be administered by a psychiatrist, doctoral level clinical psychologist, or other study staff who has extensive professional training and experience in the diagnosis of mental illness and who meets the training requirements and qualifications standards set by the Sponsor.

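### The protocol's primary endpoint, synopsis analysis and Section 8 hypotheses point to different tests, and none of the 16 unranked hypotheses (15 distinct) is marked as the one that decides the trial

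*Protocol*

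**What the plan says.** Four statements in the protocol bear on which result decides the trial.

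- **Synopsis, Primary Endpoint row.** "The primary end point is completion of 6 treatment sessions and completion of the 3 month, 6 month and 12 month follow-up assessment". The next sentence reads "Improvement of insomnia outcome is measured by Self Report Sleep Measures (SRSM". Section 8.0, Primary Objective, repeats both. The secondary endpoint and secondary objective refer only to improvement outcomes and name no measure.
- **Synopsis, Statistical Analysis row.** "Repeated measures analysis of variance (ANOVA) will be used to test Hypotheses 1, 2 and 3", and "Chi square will be used to test Hypothesis 4". Nothing beyond H4 is mentioned.
- **Section 8.0, Hypotheses.** Sixteen numbered null hypotheses stand in parallel. None is called primary, secondary or exploratory. H12 and H14 have different headings but the same overall null (12 month minus post-treatment, SRSM satisfaction sum) and the same five sub-hypotheses.
- **Section 8.0, Statistics.** "Repeated measures analysis of variance (2 X 4 ANOVA) will be used to test the Hypotheses 1-3, 5-10 and 11-16", and "Chi square will be used to test Hypotheses 4 and 11". H11 falls under both methods. The only gate lies within a hypothesis: "Any statistically significant ANOVAs will be followed by pairwise t-test comparisons to identify between group differences".

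**The concern.** A trial with several candidate results needs one named in advance as the result that answers its question. This protocol gives a primary endpoint that no hypothesis tests, names the SRSM as the measure of improvement, and supplies a synopsis analysis that leaves the SRSM out. It then supplies a full list in which nothing ranks above anything else.

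Two things are at stake. First, the conclusion is not determined. If the SRSM hypotheses were significant and H1 to H4 were not, or the reverse, the protocol could be cited for either a positive or a negative trial. Second, with many parallel overall tests and no deciding one, a chance finding on any of them can be put forward as the result.

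**Working it through.** **1. Which hypotheses belong to which statement**

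| Source | What it points to | Hypotheses |
|---|---|---|
| Primary endpoint, first sentence | Completion of sessions and follow-up | None |
| Primary endpoint, second sentence | SRSM | H5, H12, H14 by name; H6, H7, H13 by content (distress and impairment items, Appendix IX) |
| Synopsis analysis row | Sleep log, ActiWatch, Insomnia Severity Index, DSM-5 diagnosis | H1, H2, H3, H4 |
| Section 8.0 Statistics | Everything | H1 to H16 |

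The second and third rows share no hypothesis. The first row has none.

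**2. Number of distinct overall tests**

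16 listed − 1 duplicate (H14 = H12) = 15. Running the same test twice adds no error, so 15 is the right count.

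**3. Chance of at least one false positive**

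The protocol gives no significance level, power or error rate, so there is no figure of its own to reproduce. Assumptions:

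- 0.05 per overall test;
- four identical arms of 40 (160 in total, from the synopsis and Section 9.7.1);
- a common correlation ρ between outcomes, which the protocol does not give.

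If the tests are independent, the chance is 1 − (1 − 0.05)^m:

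- m = 15: 1 − 0.95^15 = 1 − 0.463 = 53.7%.
- m = 4 (H1 to H4): 1 − 0.95^4 = 1 − 0.815 = 18.5%.

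For correlated outcomes the rate was simulated. Each run used m outcomes with common correlation ρ, four groups of 40, equal means, and a one-way F test on each change score at 0.05, and counted any rejection. There were 6,000 runs per setting. A repeat with 40,000 runs agreed to within about 1.5 percentage points.

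| ρ | 15 distinct tests | H1 to H4 only |
|---|---|---|
| 0 | 54% | 19% |
| 0.3 | 47% | 17 to 18% |
| 0.5 | 37 to 38% | 15 to 16% |
| 0.7 | 26 to 27% | 13 to 14% |
| 0.8 | 22% | 12% |
| 0.9 | 14 to 15% | about 10% |

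The simulation uses an F test throughout, although H4 and H11 are assigned to chi square. The independence formula depends only on each test having size 0.05, so it is unaffected.

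A ρ of 0.5 is a reasonable middle value for some pairs. Take two changes on one instrument that share a baseline, such as H1 and H8, with equal variances and equal between-visit correlation r. Their covariance is proportional to 1 − r and each variance to 2 − 2r, so they correlate (1 − r)/(2 − 2r) = 0.5. For other pairs 0.5 is only an assumption.

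The table covers overall tests only. The lettered sub-hypotheses (35 as listed) and the six pairwise arm comparisons are left out.

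**The case against.** The strongest reply is that only the protocol is available. Significance levels and multiplicity rules are commonly left to the statistical analysis plan, so their absence is not an error. That stands. A reader might infer that the protocol tests every hypothesis at the full 5% level and so has a fixed false-positive rate of a third or more. The document does not support this: it states no level, and the rate runs from about 15% to 54% over the correlations considered.

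Three other tempting readings also fail.

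- Section 9.5.1.2 ("The efficacy assessments (CGI -S) will be administered by a psychiatrist") might look like a further set of deciding tests. It says who may administer the CGI-S and does not make the scale an endpoint for a hypothesis.
- Section 8.0 does not test everything in the same way, since H4 and H11 go to chi square.
- Not every false positive would be a false treatment effect. H15 and H16 concern satisfaction with the treatment and willingness to recommend it. H12 to H14 concern change after the end of treatment.

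It can also be said that the synopsis list is a subset of Section 8.0, using the same methods, and so is merely incomplete. That may explain how it arose. It does not remove the conflict with the primary endpoint, because the part the synopsis keeps is the part without the SRSM. An analysis plan could add an alpha rule. It could not follow a completion endpoint, an SRSM measure and an H1 to H4 analysis all at once as the basis for one conclusion.

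**Conclusion.** The point holds as an inconsistency within the protocol. The stated primary endpoint has no hypothesis, the named improvement measure is absent from the synopsis analysis, and none of the 15 distinct overall hypotheses is marked as deciding. These statements need no outside source and no assumption about the analysis plan.

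The error rates show what the missing choice could cost; they are not a property the protocol states. They rest on 0.05 per test, identical arms, 40 per arm and a common correlation. Under those assumptions even the most favourable case examined (ρ = 0.9) gives about 15% for the 15 tests, three times 5%. The synopsis set alone gives about 10%, twice 5%. A single designated test would give 5%.

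**What to change.** Change the wording in four places so that they agree: the synopsis Primary Endpoint row, the synopsis Statistical Analysis row, Section 8.0 Primary Objective and Section 8.0 Statistics.

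1. Name one confirmatory efficacy hypothesis, tested at two-sided 0.05. H5 (SRSM satisfaction sum, post-treatment minus pre-treatment) is the one consistent with the measure the protocol already names. If the sponsor prefers another, the statement about the SRSM must change with it.
2. Restate completion of sessions and follow-up as a descriptive feasibility or retention measure, not the efficacy primary endpoint.
3. Label all other hypotheses secondary or exploratory and report them with estimates and confidence intervals, unless the sponsor pre-specifies a fixed testing order. The protocol implies no order, so none is proposed here.
4. Delete H14 and list H11 under one method only.

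The cost is wording. The SRSM is already scheduled at Visits 1 and 8 (Sections 9.5.3.1 and 9.5.3.8), so no new data are needed. The downside is that results outside the confirmatory hypothesis, or outside any pre-specified sequence, can no longer be claimed as confirmatory.

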Puget Sound Psychiatry Center
[name]
[name]

**“A Randomized, Open Label, Sleep Hygiene Controlled 6-Week
Study to Compare the Efficacy of four (CBT-I, FOA, Combined
CBT-I and FOA and Sleep Hygiene) Different Behavioral
Approaches for the Treatment of Adult Subjects with
Insomnia”**

PSPC-17-01
NCT- 03461666

Protocol Date: 02-12-2018
Version 1.2

Confidentiality Statement:

This document is the property of Puget Sound Psychiatry Center (PSPC), Bothell WA and may not—in full or part—be passed on, reproduced, published, distributed, or submitted to any regulatory authority without the express written permission of PSPC.

2.0**SYNOPSIS AND SCHEDULE OF EVALUATIONS**

CLINICAL STUDY SYNOPSIS: Study PSPC-17-01	
Study Number	PSPC-17-01
Title of Study	A Randomized Open Label, Sleep Hygiene Controlled 6-Week Study to Compare the Efficacy of four (CBT-I, FOA, Combined CBT-I and FOA and Sleep Hygiene) different Behavioral Approaches for the Treatment of Adult Subjects with Insomnia.
Study Center (Country)	Puget Sound Psychiatric Center, [name](United States)
Development Phase	Prospective Study
Objective	The current study seeks to evaluate and compare the effectiveness of (1) cognitive behavior therapy for insomnia [CBT-I], (2) focus of attention [FOA], (3) a combination of cognitive behavior therapy for insomnia and focus of attention, and (4) a sleep hygiene control intervention.
Methodology	Allocation: Randomized (1; 1; 1; 1) Intervention Model: Parallel Assignment Primary Purpose: Treatment
Number of Patients	40/group or 160 totals. It is estimated that 320 prospects will need to be screened in order to have 40 per group for a total of 160 participants.

Diagnosis and Main Criteria for Inclusion.	Male and female outpatients who are 18 or older to 72 years. Insomnia Severity Index > or = 10 Meet diagnostic criteria for Insomnia Disorder per DSM-5 Willing and able to sign Informed consent form Not planning on moving away from the area for the subsequent 12 weeks.

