There will be no statistically significant overall post-treatment minus pre-treatment differences across the four treatment groups in subjective sleep measures using standardized sum scores across the four measures of self-report data from Weekly Sleep Log. If ANOVA indicates a significant overall difference, pairwise t-tests will test the following hypotheses:

Hypothesis 1a. There will be no statistically significant post-treatment minus pre-treatment mean differences across the four treatment groups in the mean number of minutes to initiate sleep (SL);

Hypothesis 1b. There will be no statistically significant post-treatment minus pre-treatment differences across the four treatment groups in the mean number of minutes to return to sleep upon awakening after sleep onset (WASO);

Hypothesis 1c. There will be no statistically significant post-treatment differences across the four treatment groups in the mean total number of minutes of sleep (TST);

Hypothesis 1d. There will be no statistically significant post-treatment minus pre-treatment differences across the four treatment groups in the mean total number of minutes of sleep divided by the total number of minutes in bed (SE).

Hypothesis 2: Treatment Effect on Objective Measures of Sleep

There will be no statistically significant overall post-treatment minus pre-treatment differences across the four treatment groups in overall objective sleep measures using standardized sum scores for data from subjects wearing an ActiWatch 2. If ANOVA indicates a significant overall difference, pairwise t-tests will test the following hypotheses:

Hypothesis 2a. There will be no statistically significant post-treatment minus pre-treatment mean differences across the four treatment groups in the mean number of minutes to initiate sleep (SL);

Hypothesis 2b. There will be no statistically significant post-treatment minus pre-treatment differences across the four treatment groups in the mean number of minutes to return to sleep upon awakening after sleep onset (WASO);

Hypothesis 2c. There will be no statistically significant post-treatment minus pre-treatment differences across the four treatment groups in the mean total number of minutes of sleep (TST);

Hypothesis 2d. There will be no statistically significant post-treatment minus pre-treatment differences across the four treatment groups in the mean total number of minutes of sleep divided by the total number of minutes in bed (SE).

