9.6 STATISTICAL METHODS AND DETERMINATION OF SAMPLE SIZE

9.7.1 SAMPLE SIZE

It is estimated that 320 prospects will need to be screened in order to have 40 per group for a total of 160 participants.

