9.7.2 ANALYSIS POPULATIONS

1. **Safety Population:** will include all randomized subjects who meet eligibility criteria and meet with their treatment provider for session 1.

2. **Intent-to-Treat Population:** will include all subjects who meet with their treatment provider for session 1 and for whom the treatment provider determines the subject meets diagnostic criteria for 780.52 Insomnia Disorder.
3. **Pre-Protocol (PP) Population:** will include all subjects who complete the 6 sessions of treatment as well as the 3 month, 6 month and 12 month follow up assessment. It is estimated that 80% of those who complete session 1 will complete session 6. It is estimated that 80% of those who complete session 6 will complete the 3 month, 6 month and 12 month follow up assessments. This will result in 25 participants who will have completed the entire study.

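### A significant four-arm ANOVA on a sum score opens pairwise t-tests on every component with no adjustment named, which does not control the familywise error once one arm differs

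*Protocol*

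**What the plan says.** The Synopsis (Methodology) randomizes equally to CBT-I, FOA, Combined and Sleep Hygiene. Section 9.7.1 plans "40 per group for a total of 160 participants".

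Section 8.0 (Statistics) names the test: "Repeated measures analysis of variance (2 X 4 ANOVA) will be used to test the Hypotheses 1-3, 5-10 and 11-16". It then gives the general follow-up rule: "Any statistically significant ANOVAs will be followed by pairwise t-test comparisons to identify between group differences".

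The composite hypotheses in section 8.0 (1, 2, 5, 7, 8, 9, 12 and 14) put the gate on one sum score. For Hypothesis 1 the ANOVA is run "using standardized sum scores across the four measures of self-report data from Weekly Sleep Log". The next step is "If ANOVA indicates a significant overall difference, pairwise t-tests will test the following hypotheses", and what follows is a list of single components: SL, WASO, TST and SE for Hypothesis 1, and five satisfaction items for Hypothesis 5.

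The omnibus test is the only protection named. The protocol gives no adjustment, no order of testing and no alpha.

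**The concern.** This is the protected least-significant-difference procedure. It holds the familywise error for three groups but not for four. With four arms, one arm that truly differs is enough to make the omnibus test significant. The three comparisons among the other arms are then each made at the full nominal level. The arm most likely to open the gate is Sleep Hygiene, which leaves CBT-I vs FOA, CBT-I vs Combined and FOA vs Combined unprotected. Those comparisons belong to the stated objective, and they carry the trial's novel claims.

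The composite structure adds to this. One significant sum score opens six pairwise tests on each of three to five components, and no component needs to pass a test of its own. A false ranking of the active treatments on some sleep measure then becomes a likely product of the analysis.

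**Working it through.** **Plan's own figures.** The protocol states no alpha, power, effect size or error rate, so there is no error figure to reproduce. Its completer count can be checked. Section 9.7.2 says "This will result in 25 participants who will have completed the entire study", and 40 × 0.8 × 0.8 = 25.6, so the 25 is a per-arm figure.

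**Inputs.**
- From the protocol: four equal arms, 40 per arm (25 completers), a gate on the sum score, four components in Hypothesis 1.
- Assumed: two-sided alpha 0.05; three equal active arms; Sleep Hygiene worse by the same amount on each measure; a common correlation between the change scores.
- Plausibility of the control difference: the Introduction cites remission of 36% with CBT-I against 16.9% in comparison conditions. On the probit scale this is −0.358 − (−0.958) = 0.60 SD. Remission is a different outcome, so this is only a rough guide, but it lies between the 0.4 and 0.8 SD used below.

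**Gate.** In a 2 × 4 repeated-measures ANOVA the group-by-time test equals a one-way ANOVA on change, here with 3 and 4 × 40 − 4 = 156 df.

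**One component, gate open.** The plain critical value is t = 1.975. At least one false difference among three equal arms has probability P(Q(3,156) > 1.975 × √2) = P(Q > 2.793) = 12.2%.

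**Four components.** There are 3 pairs × 4 components = 12 active-arm tests. If they were independent, the chance would be 1 − 0.95^12 = 46%. They are not independent, so the procedure was simulated (20,000 trials per cell):

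| n per arm | Control worse by | Correlation | Gate opens | Any false active-arm difference |
|---|---|---|---|---|
| 40 | 0.8 SD | 0.2 | 100% | about 40% (runs gave 39-41%) |
| 40 | 0.8 SD | 0.4 | 100% | 36% |
| 40 | 0.8 SD | 0.7 | 99% | 29% |
| 40 | 0.8 SD | 0.9 | 98% | 21-22% |
| 40 | 0.4 SD | 0.4 | 69% | about 28% |
| 25 | 0.8 SD | 0.3 | 99% | 38% |
| 25 | 0.8 SD | 0.7 | 92% | 29% |
| 40 | 0 (all equal) | 0.4 | 5% | about 4% |

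For five items, as in Hypothesis 5, at correlation 0.6 and 0.8 SD, the rate is 35%.

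**Number of tests.** Six pairs for each single outcome or component (9a is only a lead-in and is not counted) gives, for Hypotheses 1-3, 5-10 and 12-16: 24 + 24 + 6 + 30 + 6 + 18 + 24 + 24 + 6 + 30 + 6 + 30 + 6 + 6 = 240. Hypothesis 14 repeats Hypothesis 12 item for item, so 240 − 30 = 210 are distinct.

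**Remedies, same scenario (40 per arm, 0.8 SD, correlations 0.2-0.7).**
- Hayter's cutoff, q(0.95; 3, 156)/√2 = 2.366: about 5% on a single outcome.
- Hayter's cutoff plus a Holm-adjusted omnibus test per component: still about 13-18% over the four components. The component gates open almost as readily as the composite gate.
- Bonferroni over the 12 active-arm tests, or Hayter at 0.05/4 (|t| > 2.88): about 4-5% over the four components.

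**Cost.** The pairwise difference with 80% power is about (critical t + t at 0.80) × √(2/n).

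| Rule | n = 40 | n = 25 |
|---|---|---|
| Plain t | (1.975 + 0.844) × 0.2236 = 0.63 SD | (1.985 + 0.845) × 0.2828 = 0.80 SD |
| Hayter | (2.366 + 0.844) × 0.2236 = 0.72 SD | (2.381 + 0.845) × 0.2828 = 0.91 SD |
| Hayter at 0.05/4 | (2.881 + 0.844) × 0.2236 = 0.83 SD | (2.907 + 0.845) × 0.2828 = 1.06 SD |

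**The case against.** **Silence is not exclusion.** The protocol neither names nor rules out an adjustment, and post-hoc corrections are often left to a statistical analysis plan, which is not at hand. This is fair, and a later document could repair the rule. But the protocol does more than stay silent: it sets out the gate, the variable that carries it and the tests it opens. That procedure as written does not control the error.

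**The rates are conditional.** A reader might take 29-41% as the error rate of the plan. It is not. It needs a control arm that differs enough to open the gate, equal active arms and moderate correlations, none of which the protocol states. SE is defined from TST, so some components are structurally linked and the correlations may be high. This stands, and it is why the range is shown.

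**The time effect as a gate.** A reader might infer from "Any statistically significant ANOVAs" that a significant time main effect, which appears whenever all arms improve, would also open the pairwise tests. The documents do not support this. The composite hypotheses are worded as differences in change across the four groups, which is the group-by-time effect, and the Statistics paragraph says the pairwise tests serve to find between-group differences.

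**240 tests.** A reader might also count 240 separate tests. The duplication of Hypothesis 12 by Hypothesis 14 brings this to 210.

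**The sleep log is not the named outcome measure.** The protocol names SRSM. The same rule governs its five satisfaction items under Hypothesis 5, where the rate is similar.

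**Conclusion.** The point holds in conditional form. The follow-up procedure fixed in section 8.0 fails to control the familywise error with four arms once one arm differs. If Sleep Hygiene is clearly worse and the active arms are equal, a false difference among the active arms appears about 12% of the time on one component. On the four sleep-log components together it appears roughly three to four times in ten at correlations up to 0.7, and about one time in five at 0.9. Completer numbers do not change this materially. A smaller control difference lowers the rate but leaves it far above 5%, and the gate does its job only when all four arms are equal. These sizes rest on an assumed two-sided 0.05, the assumed control difference and the assumed correlations; the failure of the procedure does not depend on their exact values. It should be corrected before analysis, because a correction chosen after the data are seen would not be credible.

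**What to change.** 1. State alpha and sidedness, and name the group-by-time test (3 df) as the gate. This only clarifies what the hypotheses already imply.
2. For single outcomes and for the sum scores themselves, judge all six pairs against the Studentized range for three means: |t| > 2.37 at 40 per arm.
3. For components, choose one of two routes. The simpler is to report them descriptively with confidence intervals. The other is to correct across components as well, with Hayter at 0.05/4 for a four-component hypothesis (|t| > 2.88) or Bonferroni over the 12 active-arm tests. Hayter applied to all six pairs is preferable. Correcting only the active-arm tests presumes that Sleep Hygiene is the arm that differs. The 4-5% quoted for both routes belongs to the scenario above. It does not cover a component on which all four arms are equal while another component opened the gate; the descriptive route avoids that case.
4. Remove Hypothesis 14 or give it its own content.

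The change is one of wording. The cost is power. The pairwise difference detectable with 80% power rises from 0.63 to 0.72 SD at 40 per arm, and from 0.80 to 0.91 SD at 25 completers per arm. For components under the full correction it rises to about 0.83 and 1.06 SD.
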